#### **11.3.2** Urine Pharmacokinetic Parameters

Urine samples will be collected in all subjects at 5 times or time intervals during treatment with Treatments T, ST, and P: spot pre-dose (within 2 hours before dosing), 0.00 -8.00 hour, 8.00-24.0 hours, 24.0-48.0 hours, and 48.0-72.0 hours post-dose. Before starting analysis, the biostatistician will randomly select 12 evaluable subjects for whom urine and blood samples for metabolite analysis will be analyzed; the rest of the samples will be kept frozen and analyzed similarly later on if after obtaining bioanalysis results, further analysis will be needed.

The following PK parameters will be calculated for ITF2357 and its metabolites ITF2374, ITF2375, ITF2440, ITF2563, and ITF2955 glucuronidein urine:

Ae 0-t	Cumulative urinary excretion from time zero to time t, calculated as the sum of the amounts excreted over each collection interval. The amount excreted in urine for each time interval is calculated as the urine concentration multiplied by the urine volume.
R max	Maximum rate of urinary excretion, calculated by dividing the amount of drug excreted in each collection interval by the time over which it was collected.
T Rmax	Time of $R_{max}$ , calculated as the midpoint of the collection interval during which $R_{max}$ occurred.
Clr	Renal clearance, calculated as Ae 0-t /AUC 0-t (plasma)

Additional PK analysis may be performed. Upon Sponsor's request, pharmacokinetic repeats might be performed according to Syneos Health's SOP. If re-assays are requested for pharmacokinetic reasons, final results will include re-assay values, while results with original values will be presented in an appendix of the clinical study report as supportive data.

Some PK parameters may not be calculated for all or some subjects, at the discretion of the Syneos pharmacokineticist, if the concentration data is not deemed to be amenable to evaluation. Explanations for PK parameters that could not be estimated will be provided in the report.

### 11.4 Statistical Analyses

Individual and mean plasma concentration versus time curves will be presented for both linear and semi-log scales for ITF2357 and its metabolites, and moxifloxacin. Descriptive statistics (arithmetic and geometric means, SD, CV%, Min, Max, and median) of the plasma concentrations versus time will be presented as well for the PK parameters, except  $T_{max}$ , and  $T_{\frac{1}{2}}$  el.

The  $T_{max}$  and  $T_{\frac{1}{2} el}$  data will be summarized by treatment with number of observations, mean, SD, CV, Min, median, and Max.

Whenever a PK parameter can be calculated for only one period for a subject, the subject will be excluded from the statistical analysis involving this parameter. However, data from the available period will be included in the descriptive statistics.

Additional PK statistical analyses may be performed as warranted.

Italfarmaco S.p.A.

#### 12. Percentages and Decimal Places

If not otherwise specified, the following rules will be applied, with the exception of PK tables and listings described below:

Percentages will be presented to one decimal point.

Percentages equal to 0 or 100 will be presented as such without a decimal point.

Minimum and maximum will be presented with the same precision as the original values and, mean, standard deviation, and median will be presented with one more decimal place than the original values.

All digits will be used for pharmacokinetic and statistical PK calculations. For PK tables and listings, the final reportable results or data will be presented by rounding off to two decimal digits, except for the following situations (this applies to individual data and descriptive statistics):

Kel and Rsq adjusted data: rounded off to four decimal digits.

Pharmacokinetic parameters related to time such as  $T_{max}$ , must be reported with the same precision as the actual sampling time: rounded off to 3 decimal digits.

Concentration versus time data, as well as Cmax: reported as they appear in corresponding dataset.

#### 13. Handling of Missing Data

For safety,

- If an AE is recorded with an onset date corresponding to a dosing day, but the time is missing, then the AE will be assigned to the treatment phase planned treatment with a dosing planned that day.
- If an AE is recorded with an onset date that does not correspond to a dosing day, but the time is missing, then the AE will be assigned to the treatment phase planned treatment that covers the AE onset day.
- If an AE is recorded with an onset date where day and time are both missing, then the AE allocation to a treatment phase planned treatment will be done on a case by case basis considering available information (e.g. AE onset date, AE end date, AE comments, subject disposition).

For PK, only observed data will be used in the data analysis except for concentration values BLQ as described in Section 11.3. No attempt will be made to extrapolate or interpolate estimates for missing data.

For Holter, Data listings will be sorted by treatment, subject ID, and time point. Missing values will be represented by an empty cell and no imputation will be made, as described in section 10.2.1.

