9.15.2 Recording of Adverse Events

AEs will be recorded and evaluated for their seriousness, severity, and relationship to the study medication. Adverse events will be collected and documented during the course of the study, from ICF signature until a period of 12±2 days following the last study drug administration.

Adverse events will be followed-up until complete resolution, or until the Investigator judges it to be safe to discontinue follow-up. The relationship to the study medication will be classified by the Investigator according section 9.15.4.

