#### 3.4 Confinement and Washout

For each period, subjects will be confined for at least 12 hours before dosing until after the 72 hour post-dose assessments.

There will be a washout of 7 days or more between doses. The washout period may be increased for logistical considerations. Participation of each subject in this study including the screening period should last approximately 8 weeks.

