### 3.7 Subject Withdrawal and Replacement

Subjects will be advised that they are free to withdraw from the study at any time. Over the course of the study, the Sponsor and the Investigator or a Sub-investigator may withdraw any subject from the study for one of the reasons described below; subject withdrawal will be done in accordance with the clinical site's SOP:

- safety reason;
- non-compliance with protocol requirements;
- significant protocol deviation;
- positive alcohol breath test, cotinine test, drug screen, or pregnancy test;
- vomiting within 4 hours after dosing;
- marked prolongation of the QT/QTc interval (increases in QT/QTc to >500 ms or of >60 ms over baseline);
- unblinding of subjects treatment.

Italfarmaco S.p.A.

Hematology, biochemistry, coagulation (prothrombin time [PT] and partial thromboplastin time [PTT]), and urinalysis results will be reviewed by the Investigator or Sub-investigator prior to dosing; subjects will be withdrawn from the study if it is deemed that the subject's safety may be at risk on the basis of these test results.

Subjects excluded from dosing in one period as per criteria listed above, may be invited to participate in subsequent periods of the study if deemed appropriate by the Investigator and appropriate from a statistical standpoint (i.e. would permit adequate statistical comparison). However, subjects with positive alcohol, cotinine, drug screen, or pregnancy test and subjects withdrawn due to unblinding of the study treatment, will be definitively withdrawn from the study.

Subjects who withdraw or are withdrawn from the study after dosing will not be replaced. However, in the event that the number of drop-outs exceeds initial expectations, subjects who withdraw or are withdrawn might be replaced at the discretion of the Sponsor. Such replacement resulting in dosing more subjects than planned in this protocol would be documented in a protocol amendment.

Subjects who withdraw or are withdrawn will be asked to remain at the clinic until the Investigator or Sub-investigator agrees that the subject is fine and can be discharged. As soon as subject withdrawal is confirmed, blood sampling will be stopped. A PK blood draw may be collected at the time of withdrawal if deemed required by the Investigator. Study exit procedures/early termination visit will be performed at the time of withdrawal from the study or as soon as possible thereafter.

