### 9.2 Adverse Events

AEs will be recorded and evaluated for their seriousness, severity, and relationship to the study medication. Adverse events will be collected and documented during the course of the study,

from ICF signature until a period of  $12\pm 2$  days following the last study drug administration, and they will be followed-up until complete resolution, or until the Investigator judges it to be safe to discontinue follow-up.

Treatment-emergent AEs and non-TEAEs (those occurring prior to administration of study medication or that first occurred prior to study drug administration and did not worsen in frequency or severity) will be listed. TEAEs will be defined as AEs that occur on or after the date and time of study drug administration, or those that first occur pre-dose but worsen by increase in occurrence or severity after study drug administration.

The incidence of TEAEs will be summarized using the safety population. The updated version of MedDRA® dictionary will be used to classify all AEs reported during the study by SOC and PT.

Incidence of subjects who experienced TEAEs will be presented by treatment and overall, SOC, PT, by Investigator-assessed relationship and also by severity. Each subject may only contribute once to each of the incidence rates, for a TEAE following a given treatment, regardless of the number of occurrences; the highest severity or highest relationship will be presented, as appropriate. In each table, SOC will be presented in descending order of overall incidence rate in terms of frequency of subjects and then in frequency of events (alphabetical order will be used in case of equal rates). For each SOC, PT will be presented the same way.

Incidence of TEAEs (number of events) will also be presented by treatment and overall, by SOC, and PT, by Investigator-assessed relationship and severity.

Frequency of subjects experiencing Serious Treatment Emergent Adverse Events and Suspected Unexpected Serious Adverse Drug Reactions; and the number of events would be also summarized per treatment and overall. Also, these events and Serious Adverse Events will be listed per subject.

The severity of AEs will be assessed and graded according to the most recently published National Cancer Institute Common Terminology Criteria for AE (CTCAE).

The relationship of an AE or SAE to the study drug will be assessed according to the study protocol as:

- Related to study drug;
- Not related to study drug;
- Unknown.

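### SAP section 13 assigns adverse events with a missing clock time to the planned treatment, not the treatment received, so some can be counted under a treatment the subject never took

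*SAP*

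**What the plan says.** SAP section 13 has three rules for AEs with incomplete onset information.

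- Onset date is a dosing day, time missing: "then the AE will be assigned to the treatment phase planned treatment with a dosing planned that day".
- Onset date is not a dosing day, time missing: "then the AE will be assigned to the treatment phase planned treatment that covers the AE onset day".
- Day and time both missing: allocation is case by case, "considering available information (e.g. AE onset date, AE end date, AE comments, subject disposition").

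Other sections show that planned and actual treatment can differ. SAP 3.7 states: "Subjects excluded from dosing in one period as per criteria listed above, may be invited to participate in subsequent periods of the study". It also states: "Subjects who withdraw or are withdrawn from the study after dosing will not be replaced". Protocol 9.15.2 collects AEs "from ICF signature until a period of 12±2 days following the last study drug administration", and SAP 3.4 says: "There will be a washout of 7 days or more between doses".

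SAP 9.2 presents treatment-emergent AEs (TEAEs) by treatment. Each subject counts once per incidence rate for an event that follows a given treatment. SAP 8.6 lists the treatment received and the start and end times of dosing for every subject.

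**The concern.** In a crossover study the by-treatment AE table is meant to show what happened after each treatment. The first two rules in SAP section 13 depend on the randomised schedule alone. If the scheduled dose was not given, they can place an event in the column of a treatment the subject did not take, and remove it from the column of the treatment the subject did take. The event then enters a numerator to which that subject had no exposure. This is out of line with the counting rule in SAP 9.2, which concerns events that follow a treatment.

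What is at stake is the accuracy of the descriptive tolerability comparison between the two ITF2357 doses, placebo and moxifloxacin.

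**Working it through.** The documents give no figure on this point, so there is none to reproduce. The check compares the rules and then does calendar arithmetic.

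**1. The three rules side by side (SAP section 13).**

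| Onset information | Assigned by | Looks at whether the dose was given? |
|---|---|---|
| Date known (dosing day), time missing | planned treatment for that day | no |
| Date known (other day), time missing | planned treatment covering that day | no |
| Day and time missing | case by case | can do so: subject disposition is listed |

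**2. A subject who misses one period and returns.** Take sequence 5 (ST, P, T, M) from SAP Table 1 and assume doses planned 7 days apart, on days 0, 7, 14 and 21. Suppose the Period 2 placebo dose is not given and the subject returns for Period 3. Days 7 to 13 (14 − 7 = 7 days) are then covered by placebo as planned treatment, although the last dose taken was ST. An AE dated day 9 without a time is tabulated under placebo. In sequence 1 (T, ST, P, M), missing Period 2 sends the same AE to ST, although only T was taken. This case does not depend on the spacing: every day of a missed period is covered by a treatment not given.

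**3. A subject who leaves before Period 4.** Let g be the planned days between doses and F the last day of AE collection after the last dose (10, 12 or 14). The collection days on or after the next planned dosing day number max(0, F − g + 1). The documents give only a minimum for g, so the other values of g are assumptions.

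| g | F = 10 | F = 12 | F = 14 |
|---|---|---|---|
| 7 | 4 | 6 | 8 |
| 8 | 3 | 5 | 7 |
| 10 | 1 | 3 | 5 |
| 14 | 0 | 0 | 1 |

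The stated participation of about 8 weeks including screening is some guide to g. With the full 28 days of screening, three intervals, and 3 days from the Period 4 dose to Day 4, the total is 28 + 3g + 3. That is 52 days (7.4 weeks) for g = 7, 61 days (8.7 weeks) for g = 10 and 73 days (10.4 weeks) for g = 14. This favours short spacing, but a shorter screening period would leave room for longer intervals.

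**4. Direction.** The 12 sequences contain 12 × 3 = 36 steps from one treatment to the next, and each of the 12 ordered pairs occurs 3 times. Four pairs go from ITF2357 to placebo or moxifloxacin (4 × 3 = 12 steps) and four go the other way (12 steps). The remaining 12 steps are between the two ITF2357 doses or between placebo and moxifloxacin. An event could therefore move in either direction.

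**5. Size of one misassignment.** SAP 3.5 plans up to 34 subjects to ensure 28 evaluable. Taking these as the range for subjects per treatment, one subject is 1/34 = 2.9 to 1/28 = 3.6 percentage points of incidence.

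**The case against.** The strongest reply is that the wording is garbled, not wrong. The SAP does not define a treatment phase. If a phase began only with an actual dose, a missed period would have no phase and the AE would stay with the last dose taken. The counting rule in SAP 9.2 and the listing of treatment received in SAP 8.6 lean that way. However, no section says that a phase starts with a dose, and that reading leaves the word planned in the rule unexplained. A programmer following section 13 literally would use the schedule.

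The reply is stronger for early leavers. Spacing is 7 days or more and may be lengthened, so a subject who has left may have no fixed next dosing day. The follow-up call is timed from the Period 4 dose, which a leaver does not have. This part of the point is therefore possible, not certain.

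It also stands that safety results are descriptive and that dosing is listed by subject, so a misassignment could be traced.

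A reader might infer more than the documents support:

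- **That a large share of a leaver's AEs is affected.** The overlap counts calendar days. It is not a share of AEs, and it takes no account of how few AEs may lack a time.
- **That six leavers are planned for.** The difference between 34 enrolled and 28 evaluable is not a stated dropout rate, and a non-evaluable subject need not have left early.
- **That times are missing mostly for events at home, or that errors fall on safety withdrawals.** The documents say nothing on the first. On the second, SAP 3.7 also lists non-compliance, deviations, positive screens and unblinding.
- **That an AE with a recorded time is tied to the actual dose by the TEAE definition.** SAP 9.2 says "TEAEs will be defined as AEs that occur on or after the date and time of study drug administration". That settles whether an event is treatment-emergent, not which treatment it is counted under.
- **That the tables of AEs of special interest are at real risk.** Those events are reported within 24 hours and examined closely, so a missing time is unlikely.

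**Conclusion.** The point holds as a wording error in the first two rules of SAP section 13. As written, they can count an AE under a treatment the subject never received. This follows directly for a subject who misses a period and returns. For an early leaver it can follow if doses are planned about 7 to 10 days apart, and hardly at all at 14 days.

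The rules concern only AEs with a known date and a missing time. The number of such AEs in affected subjects cannot be known from the documents and is probably small. Each misassigned subject moves an incidence by about 3 to 4 percentage points, assuming 28 to 34 subjects per treatment. The primary concentration-QTc analysis is untouched. The correction is worth making because it is specific and cheap, not because a large distortion is expected.

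**What to change.** In the first two rules of SAP section 13, replace the planned treatment with the treatment actually administered. Suggested text: *An AE with a known onset date and missing onset time is assigned to the study treatment actually administered on that date or, if none was administered, to the most recent study treatment actually administered before the onset date. An AE with onset before the first dose is classed as non-treatment-emergent.*

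Keep the third rule case by case, because with the onset day missing the most recent treatment may not be determinable. Add only that the allocation is made among treatments the subject actually received.

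The cost is a short SAP wording change and the matching programming rule. No new data are needed, since treatment received and dosing dates and times are already listed under SAP 8.6.

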### 14. Data Handling

The PK plasma concentrations, safety, and tolerability data will be received as SAS® datasets from the Syneos data management facility. Screening failures and ineligible volunteer's data (subject disposition) will be received from the clinical site as source data.

#### Italfarmaco S.p.A.

### 15. Software to be Used

PK analysis will be performed using Phoenix WinNonlin® version 8.0 or higher, which is validated for bioequivalence/bioavailability studies by inVentiv. The safety data tables and listings, as well as PK tables and listings will be created using SAS®, release 9.2 or a higher version. PK figures will be created using R version 3.5 (or higher). The CSR will be created using Microsoft® Office Word 2010, or a higher version.

#### Italfarmaco S.p.A.

#### 16. Appendix A: Early Precision QT Analysis

Twelve-lead ECGs will be extracted in up to 10 replicates from each nominal time point prespecified in the protocol. The median value of each parameter from the set of evaluable beats in each extracted replicate will be calculated, and then the mean of all available medians (minimum 3 medians) from the nominal time point will be used as the subject's reportable value at that time point.

Early Precision QT analysis (formerly High Precision QT analysis) will be performed on all analyzable (non-artifact) beats in the 10 ECG replicates (1 replicate consists of one 14 second ECG). Statistical quality control procedures will be used to review and assess all beats and identify "high" and "low" confidence beats using several criteria including:

- QT or QTc values exceeding or below certain thresholds (biologically unlikely);
- RR values exceeding or below certain thresholds (biologically unlikely);
- Rapid changes in QT, QTc, or RR from beat to beat.

Placement of fiducials and measurements of all primary ECG parameters (QT, QTc, RR) in all recorded beats of all replicates will be performed using the iCOMPAS software. All beats that are deemed "high confidence" will not be reviewed by an ERT cardiac safety specialist. All low confidence beats will be reviewed manually by an ERT cardiac safety specialist and adjudicated using pass-fail criteria. The beats found acceptable by manual review will be included in the analysis. The beats confirmed to meet fail criteria will not be included in the analysis.

For the purpose of measuring PR and QRS intervals and to assess T-wave morphology and presence of U-waves, the TQT Plus algorithm will select the 3 ECG replicates with the highest quality score from the ECG extraction window. These 3 ECGs will be analyzed using a semi-automated process to determine these parameters. If 3 consecutive usable beats cannot be identified in at least 2 of the 3 replicates, then all beats in all replicates will be reviewed for that time point using a manual analysis.

If manual analysis is required, then all beats in a minimum of 3 replicates will be reviewed using the iCOMPAS software. The ERT cardiac safety specialist will review all usable beats in Lead II (or an alternate lead) for each replicate and will review and/or adjust the fiducial placements (onset of P, onset of Q, offset of S, and offset of T-wave that were electronically marked) of each waveform and also document the T wave morphology and the presence of U-waves for each beat. A replicate will only be reported if it has 3 approved, usable beats.

